8.5.1 Ancillary treatments

In addition to receiving study treatment, all patients should receive best supportive care (BSC), as per standard local practice for the treatment of pre-existing medical conditions or adverse events that may arise during the study. BSC is defined as drug or non-drug therapies, nutritional support, physical therapy or any other treatment alternative that the investigator believes to be in the patient's best interest, but excluding other antineoplastic treatments. Patients with bone metastasis should be treated additionally according to local guidelines.

All medications and non-drug therapies (including physical therapy, oxygen and blood transfusions) administered to the patient after the first dose of study treatment must be reported on the appropriate Concomitant Medication/Significant Non-Drug Therapy CRF pages throughout the study.

Patients should be instructed not to take additional medications (including over-the-counter products and herbal/alternative medications) during the study without prior consultation with the investigator).

8.5.2 Palliative radiotherapy

Palliative radiation is permitted. It should not be delivered to a target lesion.

If palliative radiotherapy is initiated, the reason for its use must be clearly documented and progression as per RECIST 1.1 must be ruled out.

No dose modification of study treatment is needed during palliative radiotherapy.

8.5.3 Permitted concomitant therapy

The patient must be told to notify the investigational site about any new medications she takes after the start of the study drug. All medications (other than study drug) and significant non-drug therapies (including physical therapy and blood transfusions) administered during the study and for up to 28 days after study drug discontinuation must be listed on the Concomitant Medications or the Procedures and Significant Non-Drug Therapies eCRF pages, respectively.

Use of supportive therapy for protocol treatment induced toxicities is permitted. Patients should receive full supportive care and palliative care (e.g. pain control) as clinically indicated during the trial, including transfusion of blood products, and treatment with antibiotics, antiemetics, antidiarrheals and analgesics when appropriate, *with the exception of the therapies mentioned in section 8.4.3.*

Palliative radiotherapy is permitted excepting extended radiatio compromising bone marrow capacity.

The first regimen of antineoplastic medication/treatments received after study treatment discontinuation must also be recorded in the eCRF antineoplastic treatment modules.

8.5.4 Prohibited concomitant therapy

Use of the following treatments is NOT allowed during the study:

- Investigational or commercial anticancer agents, such as chemotherapy, immunotherapy, targeted therapy, biological response modifiers, or endocrine therapy other than the once listed must not be given to patients.
- Hormone replacement therapy, topical estrogens (including any intra-vaginal preparations), Megestrol acetate and selective estrogen-receptor modulators (e.g. Raloxifene) are prohibited.
- Patients receiving concomitant immunosuppressive agents or chronic corticosteroids use, after taking the first dose of study drug in cases outlined below: Topical applications (e.g. rash), inhaled sprays (e.g. obstructive airways diseases), eye drops or local injections (e.g. intra-articular) are allowed. Long term low dose therapy, i.e. ≤ 10 mg/d prednisolone equivalent is permissible.
- Hematopoietic growth factors (e.g. Erythropoietins, G-CSF and GM-CSF) are not to be administered prophylactically. Use of these must be reserved to cases of Grade 3 or 4 neutropenia and anemia as per the labeling of these agents.
- Where possible, it is recommended to avoid drugs or substances known to be inhibitors or inducers of the isoenzyme CYP3A:
 - Co-administration with strong CYP3A inhibitors (e.g. Ketoconazole, Itraconazole, Ritonavir), and strong inducers (e.g. Rifampin, Rifabutin) should be avoided.
 - Co-administration with moderate CYP3A inhibitors (e.g. erythromycin, fluconazole, calcium channel blockers, benzodiazepines) and moderate inducers (e.g., carbamazepine, phenobarbital, phenytoin) should also be avoided if possible or otherwise subject to caution (e.g. increased frequency of safety monitoring).
 - Inhibitors – prohibited 7 days before dosing (6 months for amiodarone) and during protocol treatment
 - Inducers – prohibited 14 days before dosing and during protocol treatment

Sevilla orange, grapefruit and grapefruit juice affect cytochrome P450 and P-gp activity and must therefore be avoided during study drug intake.

Because the composition, pharmacokinetics and metabolism of many herbal supplements are unknown, concurrent use of all herbal supplements is prohibited during protocol treatment.

APPENDIX VI – PROHIBITED MEDICATIONS lists clinically relevant CYP3A inhibitors, inducers and the definition of strong and moderate inhibitors/inducers.

- It is to be noted that everolimus may affect the response to vaccinations making it less effective. Live vaccines must be avoided while a patient is treated with everolimus within this study.

8.6 Study Completion and post-study treatment

8.6.1 In General

Patients will be treated with the respective study drug until progression of disease, unacceptable toxicity, death, or discontinuation for any other reason. On the Conclusion Visit the treatment under study conditions ends. Therapy can be continued as clinical indicated during the follow up.

Everolimus/ribociclib cohort

Duration of everolimus/ribociclib therapy in combination with tamoxifen, anastrozole or letrozole is 12 month or until disease progression or other criteria for premature discontinuation (see section 12.1.1) occur. Patients receiving the ribociclib therapy are not allowed to be treated with tamoxifen in combination. Everolimus/ribociclib will be supplied by Novartis on study terms for the duration of the individual study participation within the off-label use. If medically indicated everolimus/ribociclib treatment may be continued during follow up and will be (within the off-label use) supplied by Novartis as well. Treatment after completion or premature discontinuation of everolimus/ribociclib (i.e. treatment in the follow-up period) is described in section 12.1.3.

Eribulin cohort

Duration of eribulin treatment is 12 months or until disease progression or other criteria for premature discontinuation (see section 12.1.1) occur. Eribulin will be supplied by Eisai on study terms for the duration of the individual study participation. If medically indicated eribulin treatment may be continued and will be (within the off-label use) supplied by Eisai as well. Treatment after completion or premature discontinuation of eribulin (i.e. treatment in the follow-up period) is described in section 12.1.3.

8.6.2 Definition of end of the study

The study end is planned for a maximum of three years after recruitment of the last patient (LPLV). Study will be

terminated after death or complete two year follow-up off all patients. Patients will be followed for safety for 28 days after the individually last dose of everolimus/ribociclib/ eribulin study drug. At the end of the study the current progression and survival status for all patients will be updated finally and recorded in the eCRF.

8.6.3 Early study termination

The sponsor can terminate the study for reasons stipulated in the clinical trial agreement. Should this be necessary, the patient should be seen as soon as possible for the final visit and the same assessments should be performed as described for a prematurely withdrawn patient. The investigator may be informed of additional procedures to be followed in order to ensure that adequate consideration is given to the protection of the patient's interests. The sponsor will be responsible for informing the ethics committee of the early termination of the trial.

8.6.4 Follow-up for toxicities

Patients whose everolimus/ribociclib treatment is interrupted or permanently discontinued due to an adverse event or abnormal laboratory value suspected to be related to study treatment must be followed at least weekly until the adverse event or abnormal laboratory values resolves or returns to grade 1. If a patient requires an everolimus/ribociclib/ eribulin dose delay of > 4 weeks from the intended day of the next scheduled dose, then the patient must be discontinued from the study.

9 EVALUATION

(cf. APPENDIX II – PATIENT EVALUATION FLOW SHEET)

9.1 Evaluation during Treatment Period

In General

With the exception of the blood samplings for circulating tumor cells and translational medical investigations, assessment of adverse events, survival, quality of life and tablet count all procedures performed during treatment period are part of the clinical routine usual in metastatic breast cancer.

Scheduled Control Visits

For all patients there is a visit every 2 – 4 weeks for Everolimus/ribociclib cohort and every 6 weeks for Eribulin cohort. The date of each Control Visit is not determined with respect to the preceding one but with regard to time since first dose of protocol treatment (± 3 , etc. days after first dose). On each visit the following procedures are carried out:

- Assessment of vital signs (heart rate, blood pressure, temperature)
- Physical examination
- Standard 12-lead ECG for ribociclib cohort
- Assessment of adverse events (see section 11)
- Documentation of protocol treatment
- Tablet count, further supply of everolimus/ribociclib if necessary (everolimus/ribociclib cohort only)
- Pregnancy test (eribulin cohort only)
- Assessment of concomitant medication (denomination, start date/end date, specification if ongoing, dosage, route)
- Blood sampling for hematology and chemistry. Analyses are to include the parameters given in TABLE 26 below.
- Assessment of quality of life by means of the EORTC QLQ-C30 and EORTC QLQ-BR23 questionnaires
- Assessment of survival

Hematology	
 - Hemoglobin - Hematocrit - Red blood cell count - Differential white blood cell count - Platelet count
Biochemistry	
 - Total and direct bilirubin - ALT/AST - GGT, AP, and LDH (ribociclib cohort only) - Serum creatinine - Albumin - BUN or urea - Sodium, potassium, calcium, phosphorous (ribociclib cohort only) - Fasting cholesterol and triglycerides (everolimus/cohort only) - Fasting glucose (everolimus cohort only) - Potassium and Magnesium (eribulin cohort only)

Table 26: Standard hematology and biochemistry

During treatment CTC determination should be performed with **Analysis Kit** at week 3 - 4 and 9 -12 (that means for the eribulin cohort after cycle 1 and 3) only in patients who have given informed consent for translational medical investigations (**TraFo-Project**).

Thereafter, CTC determination should be performed together with evaluation of therapy response (every 3 month) in the everolimus/ribociclib cohort since the correlation between CTC count and therapy response will be investigated. This procedure is part of the usual clinical routine in metastatic breast cancer.

- Tumor evaluation according to section 10.2.1
- Blood sampling with **Analysis Kit** (everolimus/ribociclib cohort only)

Assessments independent of scheduled Control Visits:

- Hematology and chemistry assessments are carried out whenever clinically indicated and when monitoring toxicities in particular (cf. section 8.2). The parameters listed in TABLE 26 are reported on the eCRF laboratory pages.
- Adverse events (cf. section 11) are assessed on each patient visit to the study site whether scheduled or not.

Conclusion Visit of the treatment period

The conclusion visit of the treatment period is performed:

- As soon as possible in case of disease progression
- As soon as possible in case of other criteria for premature discontinuation of protocol treatment (as defined in section 12.1.1.)
- After 12 months in case of no tumor progression or other criteria for premature discontinuation of protocol treatment occur

The following actions are taken:

- Assessment of vital signs (heart rate, blood pressure and body temperature)
- Physical examination
- Standard 12-lead ECG
- Assessment of adverse events (cf. section 11)
- Assessment of concomitant medication
- Documentation of end of protocol treatment and of planned therapy after end of protocol treatment
- Blood sampling for hematology and chemistry, analyses are to include the parameters given in TABLE 26.
- Blood sampling with **Analysis Kit** in all patients
- Assessment of quality of life by means of the EORTC QLQ-C30 and the EORTC QLQ-BR23 questionnaires
- Collection of unused everolimus/ribociclib, tablet count (everolimus/ribociclib cohort only)
- Pregnancy test (eribulin cohort only)
- Assessment of survival
- Reminding the patient of the planned follow-up procedures.

Protocol treatment ends with this visit and subsequent therapy is as described in section 12.1.3 “Therapy after end of protocol treatment”.

9.2 Evaluation during Follow-Up Period (after Treatment Period)

Follow-up procedures are study specific and not part of the usual routine in case of metastasizing breast cancer.

Between two and four weeks after conclusion visit of the treatment period and then at least every three months the following is assessed during routine visits in the clinical trial center or via telephone call:

- Adverse events which are \geq grade 3 NCI CTCAE and/or serious
- Concomitant medication
- Survival

Therapy during Follow-Up Period is as described in section 12.1.3 “Therapy after end of protocol treatment”.

10 **CRITERIA FOR MEASUREMENT OF STUDY ENDPOINTS**

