- Blood sampling for hematology and biochemistry (APPENDIX II)
- Blood sampling with Analysis Kit in week 3-4 and 9-12 only in patients who have given informed consent - part 3 for translational medical investigations (TraFo-Project)
- Blood sampling with Analysis Kit afterwards every 3 months in everolimus/ribociclib cohort only nse
- Tumor evaluation every 12 weeks (in the everolimus/ribociclib cohort together with blood sampling for CTC count)
- Quality of life assessment: EORTC QLQ-C30 and EORTC QLQ-BR23
- Tablet count, additional dispense of everolimus/ribociclib if necessary
- Pregnancy test (eribulin cohort only)
- Survival

Conclusion Visit of the Treatment Period

As soon as possible after disease progression, completion or premature discontinuation of protocol treatment or respectively 12 months after inclusion:

- Vital signs
- Physical examination
- Standard 12-lead ECG
- Adverse events
- Concomitant medication
- Documentation of end of protocol treatment and planned therapy after end of protocol treatment
- Blood sampling for hematology and biochemistry
- Blood sampling with Analysis Kit
- Quality of life assessment: EORTC QLQ-C30 and EORTC QLQ-BR23
- Tablet count, collection of unused everolimus/ribociclib
- Pregnancy test (eribulin cohort only)
- Survival
- Reminding patient of the follow-up procedures planned

Follow up assessments

Between 2 and 4 weeks after Conclusion Visit of the Randomized Treatment Period and then every 3 months:

- Adverse events which are \geq grade 3 NCI CTCAE and/or serious
- Concomitant medication
- Survival

Objectives and Endpoints of Clinical Trial

Primary objective:

Everolimus/Ribociclib cohort (DIVa)

The primary objective is to investigate the clinical efficacy of everolimus/ribociclib (as assessed by the CTC clearance rate) in combination with endocrine therapy in postmenopausal patients with hormone-receptor positive, HER2-negative metastatic breast cancer and persisting only HER2-negative circulating tumor cells (CTCs).

Eribulin cohort (DIVb)

The primary objective is to investigate the clinical efficacy of eribulin (as assessed by progression-free survival, PFS) both in patients with HER2-negative, hormone-receptor positive metastatic breast cancer and indication to chemotherapy and triple-negative metastatic breast cancer both with persisting only HER2-negative CTCs.

Secondary objectives:

In General

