4.3 Schedule

The individual study participation begins with the screening visit, consists of endocrine therapy plus everolimus/ribociclib or therapy with eribulin (depending on the treatment cohort) and ends with disease progression, the patient's death or with completion of the follow-up period. The estimated maximum duration of individual study participation is 36 months and 3 weeks both for the everolimus/ribociclib cohort and the eribulin cohort.

Patient participation is divided in 3 consecutive periods:

Pre-Treatment Evaluation Period:

Content:	Examinations and collection of data relevant to decide on patients' eligibility for further study participation. Informed consent 1
Period:	From screening to inclusion
Maximum duration:	3 weeks
Visits:	From Screening Visit to end of Inclusion Visit

Treatment Period:

Content:	Endocrine therapy combined with everolimus/ribociclib or chemotherapy with eribulin.
----------	--

Assessment of efficacy and safety data.
Informed consent 2 and 3

Period: From inclusion until disease progression or occurrence of other criteria for treatment discontinuation

Maximum duration: 12 months* (both for the everolimus/ribociclib cohort and the eribulin cohort) or until progress / death or discontinuation due to toxicities or other reasons

Visits: From Inclusion Visit to Conclusion Visit (4 weeks after last application of everolimus/eribulin)

*After treatment period the treatment with everolimus/ribociclib or eribulin can be extended if medically indicated. Patients will be followed up for toxicity and efficacy in such cases. The drug will be supplied by Novartis (everolimus/ribociclib), respectively Eisai (eribulin) on study terms for the duration of the individual study participation (including 2-year-period of follow-up assessments).

Follow-Up period:

[figure not shown]
Content: Assessment of survival, adverse events and concomitant medication. Treatment of the metastatic disease at the investigator's discretion

Period: From end of study treatment until the patient has either died or completed the 24-months follow-up period

Maximum duration: 24 months (estimation)

Visits: From Conclusion Visit of the Treatment Period to the last Follow-Up Visit

Figure 9: Clinical Trial Design

Entire Study:

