11 ADVERSE EVENT REPORTING

11.1 Definitions, Collection and Recording of Adverse Events by the Investigator

An adverse event (AE) is any untoward medical occurrence in a patient administered a pharmaceutical product and which does not necessarily have a causal relationship with this treatment. An adverse event (AE) can therefore be any unfavorable and unintended sign (including an abnormal laboratory finding), symptom, or disease temporally associated with the use of a medicinal (investigational) product, whether or not related to the medicinal (investigational) product. In particular this includes new findings or changes from baseline in laboratory test results or any other safety assessments (e.g. ECGs, radiological scans, vital signs assessments) felt to be clinically significant in the medical and scientific judgment of the investigator.

During treatment period AEs are collected by the investigator at least on every visit of the patient at the study site, whether it is a scheduled study visit or not.

During the follow-up period (after conclusion of the treatment period) only adverse events are collected by the investigator which are \geq grade 3 NCI CTCAE and/or serious.

Every adverse event is followed up until it has subsided or stabilized.

On each AE the following data are raised and documented by the investigator in the respective electronic case report form:

- Diagnosis or each single symptom if diagnosis is not available,
- Date and time of onset and end of AE,
- Whether onset was after the first administration of study medication (yes/no),
- Course (continuous / intermittent, if intermittent: number of episodes),
- Whether the AE is a reportable serious adverse event (serious/ non-serious, for the definition of "reportable serious event" cf. section 1.3),
- Intensity (grade 1 to 5 according to the NCI Common Terminology Criteria for Adverse events (CTCAE) version 4.03),
- Causal relationship with investigational medicinal product (no (not related) / yes (reasonable possibility)),
- Counter-measures (none/ dose reduced/ drug withdrawn/ other drug treatment/ other measures),
- Outcome (recovered/ recovering/ not recovered/ recovered with sequelae/ fatal/ unknown),

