13.1.2 Duration of Protocol Treatment

Duration of endocrine therapy:

- Depends on the occurrence of tumor progression or other criteria for discontinuation (see section 12.1.1.)
- The treatment can be extended in case of missing progress. Conclusion Visit should be performed 12 month after recruitment (End of treatment period under study conditions) or as soon as possible if criteria for discontinuation occur.

Duration of treatment with everolimus/ribociclib:

- Depends on the occurrence of tumor progression or other criteria for discontinuation (see section 12.1.1.)
- The treatment with everolimus/ribociclib can be extended if medically indicated. Conclusion Visit should be performed 12 month after recruitment even if therapy with everolimus is continued or as soon as possible if criteria for discontinuation occur.

Duration of treatment with eribulin:

- Depends on the occurrence of tumor progression or other criteria for discontinuation (see section 12.1.1.)
- The treatment with eribulin can be extended if medically indicated. Conclusion Visit should be performed 12 month after recruitment even if therapy with eribulin is continued or as soon as possible if criteria for discontinuation occur.

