13.1.3 Therapy after End of Protocol Treatment

Therapy during the follow-up period will be according to current guidelines and is at the discretion of the investigator, regardless of whether the protocol treatment could be completed as planned or had to be discontinued prematurely). The treatment with everolimus/ribociclib can be extended in case of missing progress. The drug will be supplied by Novartis on study terms for the duration of the individual study participation (including 2-year-period of follow-up assessments). In case of clinical benefit the treatment with eribulin can be continued until progression of disease; the study drug will be (within the off-label use) supplied by Eisai as well.

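### Adverse event collection narrows to grade 3+ or serious at the Conclusion Visit, which conflicts with the all-grade report due four weeks after the last dose

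*Protocol*

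**What the plan says.** **Drug may continue after the treatment period.** Section 4.3 allows everolimus, ribociclib or eribulin to be extended if medically indicated and adds: "Patients will be followed up for toxicity and efficacy in such cases". Section 13.1.3 says of everolimus and ribociclib: "The drug will be supplied by Novartis on study terms for the duration of the individual study participation", including the two-year follow-up.

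**The Conclusion Visit does not wait for the last dose.** Under section 9.1 it takes place as soon as possible after progression or premature discontinuation, or "After 12 months in case of no tumor progression or other criteria for premature discontinuation of protocol treatment occur". Section 13.1.2 is explicit: "Conclusion Visit should be performed 12 month after recruitment even if therapy with everolimus is continued". It says the same for eribulin.

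**From that visit the AE list is short.** Section 9.2 sets a first contact at two to four weeks; "then at least every three months the following is assessed during routine visits in the clinical trial center or via telephone call". The AEs listed are those of grade 3 or higher and/or serious. Section 11.1 repeats the limit: "During the follow-up period (after conclusion of the treatment period) only adverse events are collected by the investigator which are" grade 3 or higher and/or serious. The synopsis has the same list, timed "Between 2 and 4 weeks after Conclusion Visit of the Randomized Treatment Period and then every 3 months". None of the three excepts a patient still taking study drug or only just off it.

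**Other sections count from the last dose.** The synopsis (End of treatment, all cohorts), section 8.2.1.9 (everolimus) and section 8.3.1.9 (ribociclib) require a visit four weeks after the last intake to report AEs, with no grade limit. Section 8.6.2 requires safety follow-up for 28 days after the last dose. Section 13.1.1 ends all AE and SAE collection at that point. Section 4.3 describes the treatment-period visits as running "From Inclusion Visit to Conclusion Visit (4 weeks after last application of everolimus/eribulin").

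**The concern.** A site needs one answer to one question: until when are all AEs recorded? The protocol ties the answer to the Conclusion Visit in some sections and to the last dose in others. The two dates differ for any patient whose Conclusion Visit comes before the end of the 28-day window after the last dose. That includes everyone who continues drug past month 12, and also patients who stop earlier and have their Conclusion Visit promptly.

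At stake is the completeness of the safety record. Toxicity and tolerability are a stated secondary objective, and section 15.4 bases the safety assessment mainly on AE frequency. If sites resolve the conflict differently, grade 1-2 frequencies will depend partly on which section each site followed.

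**Working it through.** The protocol states no figure on this point, so the check is a comparison of text.

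**1. Which rule applies to which patient**

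| Situation | Sections 9.2, 11.1, synopsis follow-up | Synopsis end of treatment, 8.2.1.9, 8.3.1.9 | Section 13.1.1 |
|---|---|---|---|
| Stops before month 12 | Grade 3+/serious only from the Conclusion Visit, held as soon as possible after stopping | All grades, reported four weeks after last intake | Collection until 28 days after last dose, then none |
| Continues past month 12, still on drug | Grade 3+/serious only from month 12 | All grades still to be reported four weeks after the later last intake | Collection continues, since the last dose has not been taken |
| More than 28 days after last dose | Grade 3+/serious to the end of follow-up | Nothing further | None |

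The rows disagree within themselves:
- Row 1: the four-week report falls after the Conclusion Visit, inside the period where section 11.1 excludes non-serious grade 1-2 events.
- Row 2: the same exclusion applies while drug is being taken, for up to 36 - 12 = 24 months.
- Row 3: one section collects grade 3+ and serious events and another collects nothing.

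**2. Does section 4.3 settle it?** If the Conclusion Visit were four weeks after the last application, rows 1 and 2 would agree. But sections 9.1 and 13.1.2 contradict that timing, the latter expressly for patients who continue. Section 4.3 also promises toxicity follow-up during extended treatment without naming a visit, test or AE scope.

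**3. Does Appendix II settle it?** Its follow-up column ticks adverse events with no grade limit, so it sides with neither rule clearly. It schedules no examination, laboratory test or ECG in follow-up.

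**4. What is still recorded?** Sections 8.2.2.1, 8.3.2.1 and 8.4.2.1 require every interruption or dose modification to go on the dosing page. Sections 8.2.1.5, 8.3.1.5 and 8.4.1.5 require the reason for a dose change, with an adverse event or laboratory abnormality as examples. Section 8.6.4 adds weekly follow-up once everolimus or ribociclib is held for suspected toxicity. The loss is therefore the non-serious grade 1-2 entry on the AE page.

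**5. Can the number of continuing patients be bounded?** Assume exponential PFS, S(12) = 2^(-12/median), and 90 patients per drug.

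| Median PFS in the protocol | S(12) | Of 90 |
|---|---|---|
| 5.0 months (15.3, lower end; patients whose CTCs stay at 5 or more) | 0.189 | 17 |
| 7.8 months (everolimus + exemestane, local assessment) | 0.344 | 31 |
| 10.0 months (15.3, upper end) | 0.435 | 39 |
| 11.0 months (everolimus + exemestane, central assessment) | 0.469 | 42 |
| 16.0 + 9.3 = 25.3 months (ribociclib + letrozole, no prior therapy for advanced disease) | 0.720 | 65 |

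The result runs from 17 to 65 of 90 depending on the median chosen. None of these medians is stated for this trial's everolimus or ribociclib patients as a whole, and the share who would continue drug is not given. No bound follows.

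**The case against.** **After month 12 the drug is outside protocol treatment.** Sections 8.6.1 and 9.1 say that treatment under study conditions ends at the Conclusion Visit, and section 13.1.3 leaves later therapy to the investigator. A lighter record could then be deliberate. This has force for monitoring intensity. It does not remove the conflict: the four-week AE report in sections 8.2.1.9 and 8.3.1.9 is tied to last intake with no 12-month cap, section 4.3 promises toxicity follow-up in exactly these patients, and patients who stop before month 12 are affected as well.

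**A reader might infer that mandatory grade 2 dose holds go undetected and unrecorded after month 12.** The documents do not support that. Interruptions and their reasons are recorded on the dosing page. Whether the hold tables bind after the Conclusion Visit is arguable, and several defer to medical judgment. Appendix II note 20 already makes ribociclib ECGs and liver tests a matter of clinical indication after the early cycles, so their absence later is not caused by the month-12 switch. Eribulin keeps a blood count before each dose (section 8.4.1.9).

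**A reader might also put a size on the loss from the cited AE tables.** For example, stomatitis stayed at grade 1-2 in 30 - 6 = 24 of 30 patients with tamoxifen plus everolimus, and in 50 - 3 = 47 of 50 with letrozole plus everolimus. Those counts cover whole courses of treatment from its start. They show what a grade 3 limit filters out, but not how often such events arise after 12 tolerated months.

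**Conclusion.** The contradiction is real and can be read directly from the text. Followed as written, sections 9.2 and 11.1 leave non-serious grade 1-2 AEs off the AE page in two groups:
- patients who continue drug after month 12;
- patients who stop earlier, for the part of the 28 days after the last dose that follows the Conclusion Visit.

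The synopsis and sections 8.2.1.9 and 8.3.1.9 require those events to be reported, and section 13.1.1 adds a third rule.

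The effect is confined to safety data. Neither CTC clearance nor PFS is touched, serious and grade 3+ events are still collected under section 9.2, and dose interruptions are still documented. How many patients and events are involved cannot be determined from the protocol. The conclusion assumes that sites follow sections 9.2 and 11.1 and the month-12 timing of 9.1 and 13.1.2; on the timing in section 4.3 the gap would not arise. It is worth correcting because the remedy is specific and cheap.

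**What to change.** - **Sections 9.2, 11.1 and the synopsis:** state that AEs of all grades are collected until 28 days after the actual last dose of everolimus, ribociclib or eribulin, and that the grade 3+/serious list applies only after that. Make the rule cover prescribed as well as study-supplied drug. Otherwise everolimus with exemestane (section 3.2.9) and label-prescribed eribulin (section 3.4.8) would stay unresolved.
- **Section 4.3:** replace the Conclusion Visit timing with the rule in sections 9.1 and 13.1.2.
- **Section 13.1.1:** replace the statement that AE and SAE collection ends after 28 days with a reference to section 9.2.
- **Appendix II:** add a note to the follow-up column giving the same cut-off.
- **While drug continues after month 12:** record laboratory and ECG results obtained in routine care. No new tests are needed.

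The cost is a wording amendment and some additional eCRF entry for patients who continue drug.
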